9.1 Exposure

Study drug administration will be listed by subject.

9.2 Adverse Events (AEs)

AEs will be coded using the latest version of the MedDRA. Output data will include the MedDRA version 26.1 AEs will be grouped by SOC and PT and summarized by actual treatment and by overall. The summary tables will present the number and percentage of total subjects and number of events by SOC and by PT.

All AE summaries will be restricted to treatment-emergent AEs (TEAEs), defined as AEs that commence on or after the time of study drug administration. AEs without an onset date or time, or AEs with an onset date of the date of study drug administration but without an onset time, will be defined as treatment-emergent, unless an incomplete date (e.g., month and year) clearly indicates that the event started prior to administration of study drug, or the AE stop date indicates that the event started and stopped prior to administration of study drug.

The number and percentage of subjects experiencing TEAEs and the number of TEAEs will be tabulated. Subjects who experience the same TEAE (in terms of MedDRA PT) more than once will only be counted once per treatment; however, the total number of events will be counted per category. This also applies to sub-categories displayed in the summaries.

This document is confidential.

The following summaries will be presented:

- Overall summary of TEAEs
- TEAEs by SOC and PT
- TEAEs by SOC, PT, and severity
- TEAEs by SOC, PT, and relationship to study drug
- Serious TEAEs by SOC and PT
- Serious TEAEs by SOC, PT and relationship to study drug

All AEs will be listed. The following listings will be included: Non-TEAEs, TEAEs, and serious AEs.

9.1 Laboratory Evaluations

Laboratory data, including hematology, biochemistry, coagulation, and urinalysis (quantitative and categorical), will be listed by subject, and summarized by treatment and visit, categorical values less than x or greater than x will be summarized by frequency. Observed values and changes from baseline will be presented.

In addition, a shift table representing the categorical change (normal, abnormal not clinically significant, or abnormal clinically significant) from baseline to each post baseline visit will be presented by treatment.

Abnormal results will be flagged in the listings.

9.2 Vital Signs

Vital sign measurements will be listed by subject and summarized by treatment, visit and timepoint. Observed values and changes from baseline will also be presented.

In addition, a shift table representing the categorical change (normal, abnormal not clinically significant, or abnormal clinically significant) from baseline to each post baseline visit and timepoint will be presented by treatment.

Abnormal results will be flagged in the listings.

9.3 Electrocardiograms (ECGs)

Electrocardiogram (ECG) values will be listed by subject and summarized by treatment, visit and timepoint. Observed values and changes from baseline will be presented.

In addition, a shift table representing the categorical change in overall interpretation (normal, abnormal not clinically significant, or abnormal clinically significant) from baseline to each post baseline visit and timepoint will be presented by treatment.

Abnormal results will be flagged in the listings.

9.4 Physical Examination

The results of physical examinations will be listed by subject. Abnormal results will be flagged in the listings.

This document is confidential.

9.5 Injection Site Evaluation

The results of injection site evaluation will be listed by subject.

10. Changes from Analysis Planned in the Protocol

Inclusion of the randomized population

11. Programming Considerations

All TFLs and statistical analyses will be generated using SAS for Windows, release 9.4 (SAS Institute Inc., Cary, NC, USA) software. Phoenix® WinNonlin®, version 8.3.4 (Certara USA, Inc., Princeton, NJ) will be used for all PK analysis. This software was validated by Syneos in compliance with US 21 CFR Part 11 regulation.

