1.5 Benefit/Risk Assessment

The inclusion and exclusion criteria have been chosen to select subjects who are known to be free from any significant illness, history of autoimmune diseases, and from any condition that could impact their safety or interfere with meeting the study objectives. The proposed safety screening and monitoring assessments are deemed to be sufficient to monitor potential risks of AIO-001 administration. There is no anticipated therapeutic benefit for the healthy subjects in this study.

So far, as mentioned before, a total of 147 subjects received AIO-001/placebo, including 100 healthy subjects were exposed to AIO-001 or placebo (n=20) at a single dose of 50 – 600 mg, 12 patients with mild asthma received a single subcutaneous dose of 200 mg AIO-001 (n=8) AIO-001 or placebo (n=4), 24 patients with moderate or severe asthma received a single subcutaneous dose of 100/600 mg AIO-001 (n=16) or placebo (n=8), and 11 patients with severe asthma received multiple subcutaneous doses of [REDACTED] mg AIO-001 or placebo. [REDACTED]

All the safety data obtained so far was with AIO-001 using Formulation A. Although this is the first time the new Formulation (Formulation B) will be tested in humans, this study will evaluate Formulation B, and a similar safety profile is expected. All excipients are generally recognised as safe. The information obtained in this study may help in the treatment of future patients with severe, uncontrolled asthma.

2. Objectives

Primary objective:

- To compare the safety and tolerability of 400 mg of AIO-001 as the new formulation (Formulation B) with a 400 mg dose of AIO-001 administered as the original formulation (Formulation A) in healthy volunteers.

Secondary objectives:

- To evaluate the PK of a single SC AIO-001 dose of Formulation A in healthy volunteers.
- To evaluate the PK of a single SC AIO-001 dose of Formulation B in healthy volunteers.
- To evaluate the immunogenicity of AIO-001 in healthy volunteers.

3. Endpoints

Primary endpoints:

- Adverse events (AEs), vital signs measurements (blood pressure, heart rate, respiratory rate, and tympanic temperature), 12-lead electrocardiogram (ECG) recordings, physical examinations, and clinical laboratory test results, including hematology, biochemistry, and urinalysis.

Secondary endpoints:

- PK endpoints may include but are not limited to AIO-001 concentrations, $AUC_{0-\text{last}}$, $AUC_{0-\text{inf}}$, C_{\max} , T_{\max} , $T_{1/2}$.

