8.2.3 Injection Site Evaluation

Local reactions at the injection site will be evaluated by a trained observer before dosing on Visit 2 (Day 1 and approximately 1, 12, 24 hours (Day 2), 48 hours (Day 3)), 72 hours (Day 4, Visit 3) and 96 hours (Day 5, Visit 4) post-dose. A global severity rating for injection site reactions will be included in the assessment of AEs. An injection site examination post-dose will consist of examining the injection site and making note of the presence of any skin reactions, disturbances, or discolorations which will be graded and reported as per the table below:

Table 3. Injection Site Reaction Scores

Local Reaction to Injectable Product	Mild (Grade 1)	Moderate (Grade 2)	Severe (Grade 3)
Pain	Does not interfere with activity	Repeated use of non-narcotic pain reliever > 24 hours or interferes with activity	Any use of narcotic pain reliever or prevents daily activity
Tenderness	Mild discomfort to touch	Discomfort with movement	Significant discomfort at rest
Erythema/Redness*	2.5-5 cm	5.1-10 cm	> 10 cm
Induration/Swelling**	2.5-5 cm and does not interfere with activity	5.1- 10 cm or interferes with activity	> 10 cm or prevents daily activity

* In addition to grading the measured local reaction at the greatest single diameter, the measurement should be recorded as a continuous variable.

** Induration/Swelling should be evaluated and graded using the functional scale as well as the actual measurement.

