8.3.3 Assessment of Severity

The severity of AEs will be described and documented using the following definitions:

Table 5. Severity of Adverse Events

Severity	Description
Mild (Grade 1)	Awareness of signs and symptoms but are easily tolerated; are of minor irritant type; causing no limitations of usual activities. Signs or symptoms may require minor action.
Moderate (Grade 2)	Discomfort severe enough to cause some limitations of usual activities and may require action.
Severe (Grade 3)	Incapacitating with inability to carry out usual activities or significantly affects clinical status and requires specific action and/or medical attention.

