9.5 Safety and Tolerability Analysis

Demographic parameters will be summarized descriptively.

Safety and tolerability analysis will be performed for all subjects in the safety population. No inferential statistical analysis of safety data is planned.

Safety and tolerability of AIO-001 will be evaluated through the assessment of AEs (i.e., seriousness, severity, relationship to the study drug, outcome, duration, and management), vital signs, 12-lead ECGs, clinical laboratory tests, and physical examinations. AEs will be coded using the latest version of the Medical Dictionary for Regulatory Activities (MedDRA).

TEAEs will be tabulated by treatment. Changes from baseline values in vital signs, 12-lead ECGs, and clinical laboratory tests will be evaluated. Safety and tolerability data will be reported using descriptive statistics.

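### SAP 9.5 plans only a by-subject listing of injection-site results, so the Table 3 grades by sign and the recorded diameters have no summary by formulation

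*SAP*

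**What the plan says.** The primary objective (Protocol section 2, repeated in SAP section 2) begins "To compare the safety and tolerability of 400 mg of AIO-001 as the new formulation (Formulation B" and names the original Formulation A as comparator. Under Protocol 6.4, Group A receives four 1.0 ml injections and Group B two 1.1 ml injections at a higher concentration.

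Protocol 8.2.3 has a trained observer grade four local signs on Table 3: pain, tenderness, erythema and induration. The erythema footnote adds: "In addition to grading the measured local reaction at the greatest single diameter, the measurement should be recorded as a continuous variable". The induration footnote says: "Induration/Swelling should be evaluated and graded using the functional scale as well as the actual measurement". The same section links these findings to adverse events: "A global severity rating for injection site reactions will be included in the assessment of AEs".

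SAP 9.5 then reads, in full: "The results of injection site evaluation will be listed by subject".

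Injection site evaluation is not named among the primary endpoints. In Protocol section 3 and SAP section 4 that list runs from adverse events and vital signs to "12-lead electrocardiogram (ECG) recordings, physical examinations, and clinical laboratory test results, including hematology, biochemistry, and urinalysis". It is also absent from the assessments in Protocol 9.5, whose list ends "outcome, duration, and management), vital signs, 12-lead ECGs, clinical laboratory tests, and physical examinations". Protocol 9.5 does, however, promise descriptive statistics for safety and tolerability data in general.

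**The concern.** The two regimens differ in concentration, volume per injection and number of injections, so local reactions bear directly on the tolerability comparison. Protocol 1.5 says that Formulation B has not been given to humans before, and Protocol 1.4 says that it is meant for a proposed phase 2 trial. The protocol takes the trouble to grade reactions by sign and to measure them, yet the SAP makes no by-formulation summary of either.

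Anyone wanting to say how the formulations compared on worst grade or on reaction size would have to count from a listing. The counting rule (worst or first grade, which times, how to combine several sites) would then be chosen after the data are visible, in an open-label study.

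**Working it through.** No stated figure exists to reproduce: SAP 3.1 reports no sample size calculation, and SAP section 9 plans no inferential analysis of safety. The check is a comparison of planned outputs.

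**1. Which safety data are summarized by formulation?**

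| Data | SAP section | Listing | Summary by treatment |
|---|---|---|---|
| Adverse events | 9.2 Adverse Events | yes | yes |
| Laboratory | 9.1 Laboratory Evaluations | yes | yes |
| Vital signs | 9.2 Vital Signs | yes | yes |
| ECG | 9.3 | yes | yes |
| Physical examination | 9.4 | yes | no |
| Injection site evaluation | 9.5 | yes | no |

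No other SAP section summarizes Table 3 grades or diameters.

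**2. What do the TEAE tables carry?** SAP 9.2 (Adverse Events) tabulates TEAEs by system organ class, preferred term and severity, by actual treatment. Because the global severity rating enters the AE assessment, an injection-site event does appear there by formulation with a mild, moderate or severe category. If reactions are recorded sign by sign, the preferred term may also show the sign. The tables carry no diameter and no evaluation time, and only one category per event.

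**3. Is that category the Table 3 grade?** Protocol 8.2.3 does not say. Tables 3 and 5 both use Mild/Moderate/Severe (Grade 1/2/3), with different content:
- Table 3 grades erythema by diameter alone, and over 10 cm is Grade 3. Pain and induration are graded partly by interference with activity, which is closer to Table 5.
- Table 5 grades by limitation of activities. Its Mild row includes "causing no limitations of usual activities", and also requires that the event be easily tolerated and of a minor irritant type.

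Redness over 10 cm that limits nothing is Grade 3 on Table 3. It could be recorded as Mild on Table 5 if it was also judged easily tolerated. The two scales can therefore disagree, most clearly for erythema.

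**4. How much is left to the listing?** Inputs: 8 subjects per formulation (SAP 3.3), 6 post-dose times (1, 12, 24, 48, 72 and 96 hours, Protocol 8.2.3) and 4 signs (Table 3). Assume one score per subject, sign and time:
- Grades: 8 × 6 × 4 = 192 per formulation, or 384 in all.
- Erythema diameters: up to 8 × 6 = 48 per formulation.

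The documents do not say whether scoring is per subject or per injection site. Per-site scoring would give more values, and nothing below depends on it. Under either unit, the number of planned by-formulation summaries is zero.

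**5. What resolution would a summary have?** 1/8 = 12.5 percentage points per subject.

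**The case against.** The strongest reply is that this is a matter of presentation. Injection site evaluation is not a named endpoint. Physical examination, which is one, is also listed only. With 16 subjects a listing can be read by eye, and SAP 5.1 sorts listings by treatment first. Reactions recorded as adverse events are already tabulated by formulation with a severity. The table shells are a separate document, and SAP 5.2 has general rules for summarizing continuous and categorical variables.

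Much of this stands, and it rules out four stronger readings that a reader might infer:
- **That the TEAE tables carry no severity for local reactions.** They do, through the global severity rating.
- **That reactions will be missed.** The adverse event definition in Protocol 8.3.1 is broad, and nothing in the documents shows an undercount.
- **That the SAP breaches the protocol.** The general promise of descriptive statistics in Protocol 9.5 favours a table, but the named lists omit this assessment.
- **That 4 sites against 2 must by itself separate the groups.** The documents give neither a per-site risk nor the dependence between sites in one subject, so no size can be put on this. It supports a footnote only.

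The rest does not answer the point. Sorting is not a summary, and SAP 11.2.5.3 gives a different default order, by subject number. The rules in SAP 5.2 apply unless otherwise stated and mainly set format, so they do not clearly override a section that specifies a listing. Unseen shells do not change the SAP text.

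**Conclusion.** The point holds as a low-cost improvement to how the trial answers its primary question. SAP 9.5 leaves the Table 3 grades by sign and the recorded diameters without any by-formulation summary. The TEAE tables replace them only in part: one severity category per event, on an unstated scale, with no size. No effect estimate or bias can be attached to this gap.

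The conclusion rests on the SAP text alone; the shells and the case report form were not available. Continuous recording is explicit for erythema. For induration the footnote asks for grading on the measurement, which does not establish that the diameter is captured as a number.

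**What to change.** In SAP 9.5, add one descriptive table by formulation for the safety population:
- n (%) of subjects by worst post-dose Table 3 grade, overall and for each of the four signs, with a row for no graded reaction (Table 3 starts at Grade 1, which for erythema means 2.5 cm);
- descriptive statistics of each subject's maximum erythema diameter, and of maximum induration diameter if it is captured as a measurement;
- a footnote that Group A has 4 injection sites and Group B has 2, so the table compares whole regimens.

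Taking the worst value per subject works whether scoring is per site or per subject. No test or confidence interval is needed. Also state whether the global severity rating follows Table 3 or Table 5.

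The cost is one extra table and a few lines of SAP text. The grades and erythema diameters are already required by Protocol 8.2.3. The drawback is coarse estimates at 8 subjects per group.

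A separate minor point is that the evaluation times must be reconciled. Protocol 8.2.3 lists six post-dose evaluations, the first at about 1 hour. Table 1 has no 1-hour column and, as far as its extracted row can be read, shows four post-dose marks.

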11.1 General Considerations

- One SAS program can create several outputs.
- Each output will be stored in a separate file.
- Output files will be delivered in rich text format that can be manipulated in MS Word.
- Numbering of TFLs will follow International Council for Harmonisation of Technical Requirements for Pharmaceuticals for Human Use (ICH) guideline E3^a.

11.2 Table, Listing, and Figure Format

11.2.1 General

- TFLs will be produced in landscape format. The orientation may be changed to portrait, as necessary to allow additional rows to be presented.
- TFLs will be produced using the Times New Roman font, size 10. The font size may be reduced as necessary to allow additional columns to be presented, but not at the expense of clarity.
- The data displays for all TFLs will have a minimum blank 1-inch margin on all four sides.
- Unless otherwise specified, TFLs will be in black and white (no color).
- Specialized text styles, such as bolding, italics, borders, shading, and superscripted and subscripted text, will not be used in the TFLs, unless otherwise specified. On some occasions, superscripts 1, 2, or 3 may be used; see below.
- Standard keyboard characters will be used in the TFLs. Special characters, such as non-printable control characters, printer-specific, or font-specific characters, will not be used. Hexadecimal-derived characters will be used, where possible, if they are appropriate to help display math symbols (e.g., μ). Certain subscripts and superscripts (e.g., cm^2 , C_{max}) will be employed on a case-by-case basis.
- TFLs will be produced using sentence case, unless otherwise specified.

This document is confidential.

11.2.2 Headers and Footers

- Times New Roman font, size 10 will be used for TFL headers and footers.
- All outputs will have the following at the top of each page: Aiolos Bio, Inc. Aiolos Bio, Inc. Protocol AIO-001-101.
- All outputs will have page x of y at the top or bottom right corner of each page. TFLs are individually paginated in relation to total length (i.e., the page number appears sequentially as page x of y, where y is the total number of pages in the output).
- The date and time the output was generated will appear, along with the program name, at the bottom of each page.

11.2.3 Display Titles

Each display title includes the appropriate designation (“Table”, “Figure”, or “Listing”) and a numeral, along with a descriptive name (e.g., Table 14.1-1 Subject Enrollment and Disposition). ICH E3 numbering is strongly recommended, but Sponsor preferences are obtained for final determination. Display titles are left aligned, single spaced, and presented in title case. A solid line spanning the margins will separate display titles from column headings.

11.2.4 Column and Row Headings

- Column and row headings are presented in title case, with the exception of complete sentences, which will be presented in sentence case.
- Column and row headings will include “Unit” for numeric variables, as appropriate.
- Column and row headings will include the number of subjects in the analysis population for each group, presented as (N=xx). This is different from the ‘n’ used in descriptive statistics, which represents the number of observations.
- The order of treatments in the tables and listings will be Treatment A followed by Treatment B, with “overall” (if applicable) last.

11.2.5 Body of the Data Display

11.2.5.1 General Conventions

Data in columns of a table or listing are formatted as follows:

- Alphanumeric values are left aligned.
- Whole numbers (e.g., counts) are right aligned.

11.2.5.2 Table Conventions

- Units will be included, where available.

This document is confidential.

- If the categories of a parameter are ordered, all categories between the maximum and minimum category are presented in the table, even if n=0 for all groups in a category between the minimum and maximum level for that parameter. See the example for the frequency distribution for symptom severity below. If percentages are presented in these tables, 0% will not be presented, therefore, counts of zero will be presented as “0”, not “0 (0%)”.

Severity Rating	N
Severe	0
Moderate	8
Mild	3

- Where the categories are not ordered (e.g., Reason for Discontinuation), only those categories for which there is at least one subject represented will be included.
- An “Unknown” or “Missing” category will be added to each parameter for which information is unavailable for one or more subjects.
- Probability values (p-values) are presented in the format: 0.xxxx, where xxxx is the value. If the p-value is less than 0.0001, it will be presented as “<0.0001.” If the p-value is >0.999, it will be presented as “>0.999.”
- Percentage values are presented in parentheses with no spaces, one space after the count [e.g., 7 (12.8%), 13 (5.4%)]. Unless otherwise noted, for all percentages, the denominator will be the number of subjects in the analysis population for the group that has an observation. Percentages after zero counts are not displayed, and percentages equating to 100% are presented as “100%” (without decimal places).
- Unless otherwise noted, tabular displays of data for medical history, prior/concomitant medications, and AEs data are presented in alphabetical order.
- The percentage of subjects is typically calculated as a proportion of the number of subjects assessed in the relevant group (or overall) for the analysis population presented; however, careful consideration is required in many instances, due to the complicated nature of selecting the denominator. Details of this will be presented in footnotes or programming notes.
- In categorical summaries where a subject can be included in more than one category, a footnote or programming note will specify whether the subject is included in the summary statistics for all relevant categories or just one category and the criteria for selecting the category.
- Where a category with a subheading (such as system organ class [SOC]) must be split over more than one page, present the subheading followed by “(cont.)” at the top of each subsequent page. The overall summary statistics for the subheading will only be presented on the first relevant page.

